13.2 Primary Efficacy Endpoint(s)

The primary efficacy endpoint is:

- The change from baseline (prior to BMN 270 infusion while receiving FVIII prophylaxis) in the annualized number of bleeding episodes requiring exogenous FVIII replacement treatment (annualized bleeding rate, ABR for treated bleeds) in the efficacy evaluation period (“Post FVIII Prophylaxis to Last Visit”)

The annualized number of bleeding episodes for treated bleeds, or annualized bleeding rate for treated bleeds (ABR for treated bleeds) is defined as

$$\frac{\text{Number of bleeding episodes for treated bleeds during the calculation period}}{\text{Total number of days during the calculation period}} \times 365.25$$

The primary analyses for the primary endpoints will be performed on the Study 270-902 rollover subjects.

The calculation period in these formulas for the post-baseline value is:

- For the primary analysis, the efficacy evaluation period (“Post FVIII Prophylaxis to Last Visit”) as defined in Section 13.1.
- For the supportive analyses, the efficacy periods as defined in Section 13.1.

The calculation period for the baseline value is defined in the following:

- For the primary analysis, the calculation period is approximately 6 months in the non-interventional study 270-902; i.e., the baseline values will be derived from the prospectively collected 6-month data in 270-902 up until the BMN 270 infusion date in 270-301.
- For the sensitivity analysis, the calculation period is approximately 12 months prior to study screening up until the BMN 270 infusion date in 270-301. For subjects enrolled from Study 270-902, these 12 months of data consist of approximately 6 months of data prospectively collected during 270-902, together with the preceding historical data prior to 270-902 enrollment. For subjects not entering from 270-902, the 12-month historical data prior to 270-301 study screening up until the BMN 270 infusion date will be used.

For the primary efficacy endpoint, only treated bleeds will be considered. Bleeds due to surgery/procedure are not included in the primary efficacy endpoint. Only treatments that were recorded as “treatment for bleed” are included in the determination of a treated bleed.

The definition of a “treated bleed” is as follows:

Study 270-301 Statistical Analysis Plan

- If a bleed is directly followed by a hemophilia medication reported to be a “treatment for bleed” within 72 hours (or 3 calendar days if time is not available), it is considered to be a treated bleed. This bleed and the first treatment thereafter are referred to as a pair.
- If multiple bleeds of different type or/and different anatomical location occur within 24 hours (of the last bleed before treatment for bleed) or on the same calendar day, the subsequent treatment within 72 hours (or 3 calendar days if time is not available) is considered to pair with each of these bleeds. Each of these bleeds that is within 72 hours (or 3 calendar days if time is not available) of the subsequent treatment is therefore considered to be a treated bleed.
- Two bleeds of the same type and at the same anatomical location are considered to be one bleed if the second occurs within 72 hours (or 3 calendar days if time is not available) from the last treatment for the first bleed. The last treatment is defined as the last treatment before a new bleed occurs, either in the same or in a different location. This is regardless whether the second bleed is followed by a treatment.

13.2.1 Primary Estimand

The estimand formulation for the primary efficacy endpoint is as follows:

Treatment

(BMN 270 gene therapy + rescue therapy) vs. (FVIII prophylaxis + rescue therapy)

The rescue therapy for the BMN 270 gene therapy includes FVIII infusions for different purposes (routine prophylaxis, one-time prophylaxis, treatment for bleeds, and for surgery/procedure) and the emicizumab prophylaxis for hemophilia A.

The rescue therapy for FVIII prophylaxis includes FVIII infusions for other purposes (one-time prophylaxis, treatment for bleeds, and for surgery/procedure).

Population

HIV-negative subjects with severe hemophilia A

Variable (endpoint)

ABR (treated bleeds)

	Study 270-301 Statistical Analysis Plan
---	--

Intercurrent events and strategies

Intercurrent Events		Strategies for Addressing Intercurrent Events				
		Treatment Policy Strategy	Hypothetical Strategies	Composite Variable Strategies	While-on-Treatment Strategies	Principal Stratum Strategies
Death (unrelated to study drug)					✓	
Lost to follow-up					✓	
FVIII infusions	Started routine prophylaxis	✓				
	One-time prophylaxis	✓				
	Treatment for bleeds	✓				
	For surgery/procedure	✓				
	Started emicizumab prophylaxis	✓				

Population-level summary

Mean ABR (treated bleeds) change from baseline

13.2.2 Primary Analysis Method for Primary Efficacy Endpoint

The primary analysis for change from baseline in ABR for treated bleeds will be based on the Study 270-902 rollover subjects. Change from baseline in ABR (ie. post-baseline ABR – baseline ABR) will first be tested for non-inferiority with a NI margin of 3.5 using the confidence interval approach. The non-inferiority test hypotheses are:

H_0 (null hypothesis): Change ≥ 3.5 versus H_1 (alternative hypothesis): Change < 3.5 .

Assuming a t distribution with the variance estimated from the data, a two-sided $(1-\alpha)*100\%$ confidence interval (CI) of the mean change will be constructed, where the significance level α is determined by the fallback procedure. See Section 13.7 for details. If the upper bound of the CI is less than 3.5, the null hypothesis will be rejected and the non-inferiority of BMN270 versus FVIII prophylaxis in ABR with this margin will be declared. Subsequently, superiority will be assessed using the same CI. The two-sided p-value for superiority will be obtained through a one-sample t-test to test the null hypothesis that the change is 0 or greater.

If the value is missing, e.g., when a subject drops out before Week 5, the change in ABR will be imputed as the median value of the changes of all subjects’ observed cases. See Table 13.2.4.1 for sensitivity analyses with other missing data imputation methods.

13.2.3 Supportive Analysis Methods for Primary Efficacy Endpoint

The number of bleeding episodes will be listed by subject and by periods (pre-BMN 270 infusion[baseline period], Weeks 1-4, Week 1 to end of original FVIII prophylaxis, Post FVIII Prophylaxis-52, Weeks 53-104, and the efficacy evaluation periods as defined in (Table 13.1.1), and the ABR for treated will be summarized descriptively.

**Study 270-301 Statistical Analysis Plan**

The analysis of change from baseline in ABR for treated bleeds will also be conducted using data in the efficacy evaluation periods as defined in [Table 13.1.1](#).

13.2.4 Sensitivity Analysis Methods for Primary Efficacy Endpoint

The primary analysis will be conducted for the PP population when applicable.

If a subject restarts FVIII prophylaxis, starts emicizumab, or discontinues from the study prior to the cut-off for the analysis, a sensitivity analysis will be performed where the post-baseline ABR for treated bleeds is imputed as the same as the baseline ABR for treated bleeds (ie, the change in ABR is 0).

The primary analysis will also be performed with baseline (prior to BMN 270 infusion while receiving FVIII prophylaxis) values calculated using the data starting from 12 months prior to study enrollment. P-values will be provided for descriptive purpose only.

The ABR for treated bleeds will be analyzed using a generalized linear mixed model assuming negative binomial as the underlying distribution. The model will include period (pre-BMN 270 infusion [baseline period], Weeks 1-end of FVIII Prophylaxis, Post FVIII Prophylaxis-Last Visit) as the only factor. The analysis will be performed using the SAS GENMOD procedure where the duration of each period is included as an OFFSET to account for varying follow-up times and a REPEATED statement is included to account for the intra-patient comparison. In addition, the change from baseline (prior to BMN 270 infusion while receiving FVIII prophylaxis) in the ABR for treated bleeds in the efficacy evaluation period ("Post FVIII Prophylaxis to Last Visit") will also be tested using Wilcoxon signed-rank test.

The details of the sensitivity analyses are listed in [Table 13.2.4.1](#).

	Study 270-301 Statistical Analysis Plan
---	--

Table 13.2.4.1: Primary and Sensitivity Analyses of Primary Efficacy Endpoints

Endpoint	Analysis	Analysis population	Analysis period	Imputation	Analysis method
The change from baseline in the ABR for treated bleeds during Post FVIII Prophylaxis- last visit by the data cut-off for the 2-year analysis post-BMN 270 infusion	Primary	Study 270-902 rollover subjects	Baseline: Day 1 visit in 270-902 to BMN 270 infusion in 270-301 (approximately 6 months) On study: starting from week 5 post-BMN 270 dosing (Study Day 33) or 3 days after the end of FVIII prophylaxis, whichever is later, until subjects complete the study, reach the last visit by data cut-off for the analysis, or withdraw from the study (ETV), whichever is the earliest.	If ABR for treated bleeds Post FVIII Prophylaxis period is missing, the change in ABR will be imputed as the median value of the changes of all subjects’ observed cases (This was for planning purposes. Since all subjects have Post FVIII Prophylaxis ABR for treated bleeds data, no imputation will be carried out).	2-sided t-test
	Sensitivity analysis 1	Per-protocol population	Same as primary	Same as primary	Same as primary
	Sensitivity analysis 2	Same as primary	Baseline: 6 months prior to Day 1 visit in 270-902 to BMN 270 infusion in 270-301 (approximately 12 months) On-study: same as primary	Same as primary	Same as primary
	Sensitivity analysis 3	Same as primary	same as primary	Same as primary	Negative binomial regression model
	Sensitivity analysis 4	Same as primary	same as primary	Same as primary	Wilcoxon signed-rank test
	Sensitivity analysis 5	Same as primary	same as primary	If a subject restarts FVIII prophylaxis or starts emicizumab, the change in ABR for treated bleeds will be imputed as 0.	Same as primary

Study 270-301 Statistical Analysis Plan

13.3 Secondary Efficacy Endpoints

The first-ranked secondary efficacy endpoint is:

- The change from baseline (assuming no treatment for severe hemophilia A) in FVIII activity, as measured by chromogenic substrate assay, at Weeks 104 post-BMN 270 infusion

Each subject's FVIII activity level at Week 104 is defined as the median of the values obtained at Week 104 with the window defined in Appendix 20.1. The baseline value will be imputed as 1 IU/dL, since there will be no washout of severe hemophilia A subjects' usual FVIII prophylaxis (in order to avoid increasing the risk of bleeding) prior to BMN 270 infusion. Post-BMN 270 infusion values for FVIII activity will be excluded from analysis if obtained within 72 hours (or 3 calendar days if time is not available) since the last infusion of exogenous FVIII replacement therapy.

The second-ranked secondary efficacy endpoint is:

- The change from baseline (prior to BMN 270 infusion while receiving FVIII prophylaxis) in the annualized utilization (IU/kg/year) of exogenous FVIII replacement therapy in the efficacy evaluation period ("Post FVIII Prophylaxis to Last Visit")

The annualized utilization (IU/kg/year) of exogenous FVIII replacement therapy is defined as

$$\frac{\text{Sum of FVIII use (IU/kg) during calculation period}}{\text{Total number of days during the calculation period}} \times 365.25$$

The primary analyses for the annualized utilization (IU/kg/year) of exogenous FVIII replacement therapy will be performed on the Study 270-902 rollover subjects.

The calculation period in these formulas for the post-baseline value is:

- For the primary analysis, the efficacy evaluation period ("Post FVIII Prophylaxis to Last Visit") as defined in Section 13.1.
- For the supportive analyses, the efficacy periods as defined in Section 13.1.

The calculation period for the baseline value is defined in the following:

- For the primary analysis, the calculation period is approximately 6 months in the non-interventional study 270-902; i.e., the baseline values will be derived from the prospectively collected 6-month data in 270-902 up until the BMN 270 infusion date in 270-301.

Study 270-301 Statistical Analysis Plan

- For the sensitivity analysis, the calculation period is approximately 12 months prior to study screening up until the BMN 270 infusion date in 270-301. For subjects enrolled from Study 270-902, these 12 months of data consist of approximately 6 months of data prospectively collected during 270-902, together with the preceding historical data prior to 270-902 enrollment. For subjects not entering from 270-902, the 12-month historical data prior to 270-301 study screening up until the BMN 270 infusion date will be used.

The third-ranked secondary efficacy endpoint is:

- The change from baseline (prior to BMN 270 infusion while receiving FVIII prophylaxis) in the annualized number of bleeding episodes irrespective of exogenous FVIII replacement therapy (annualized bleeding rate, ABR for all bleeds) in the efficacy evaluation period (“Post FVIII Prophylaxis to Last Visit”)

The annualized number of bleeding episodes for all bleeds, or annualized bleeding rate (ABR for all bleeds) is defined as

$$\frac{\text{Number of bleeding episodes for all bleeds during the calculation period}}{\text{Total number of days during the calculation period}} \times 365.25$$

The primary analyses for ABR for all bleeds will be performed on the Study 270-902 rollover subjects. The calculation periods for the baseline and post-baseline values are similar as the periods of the ABR for treated bleeds

The fourth-ranked to seventh-ranked secondary efficacy endpoints are:

- The change from baseline (assuming no treatment for severe hemophilia A) in Haemo-QoL-A Total score, at Week 104 post-BMN 270 infusion
- The change from baseline (assuming no treatment for severe hemophilia A) in Haemo-QoL-A Physical Functioning domain score, at Week 104 post-BMN 270 infusion
- The change from baseline (assuming no treatment for severe hemophilia A) in Haemo-QoL-A Consequences of bleeding domain score, at Week 104 post-BMN 270 infusion
- The change from baseline (assuming no treatment for severe hemophilia A) in Haemo-QoL-A Role functioning domain score, at Week 104 post-BMN 270 infusion

The primary analyses of Haemo-QoL-A Total score and each domain score above will be performed on the mITT population.

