Official Title: A Phase 3, Open-Label, Single-Arm Study To Evaluate The Efficacy And Safety Of BMN 270, An Adenovirus-Associated Virus Vector-Mediated Gene Transfer Of Human Factor VIII In Hemophilia A Patients With Residual FVIII Levels ≤ 1 IU/dL Receiving Prophylactic FVIII Infusions

NCT Number: NCT03370913

Applicant/MAH: BioMarin Pharmaceutical Inc.

Version Date: 13 Dec 2021

Note to File (NTF)

Project No.:	BMN 270; Study 270-301
Project Name (If Applicable):	To align the 270-301 Protocol (version 7.0, 15 July 2021; US-specific) and the 2-year analysis SAP (version 2.0, 13 December 2021) with the 2-year 270-301 CSR
Location:	NA
Subject:	NTF to bridge the 270-301 protocol (version 7.0, 15 July 2021; US-specific) and the 2-year analysis SAP (version 2.0, 13 December 2021) with the 2-year 270-301 CSR for primary and secondary endpoints and other changes made to the 2-year analyses.
Date	02 March 2023

Overserved Discrepancy – Primary and secondary endpoints and statistical analysis methods used in the 2-year 270-301 CSR were modified from those specified in the effective versions of the 270-301 protocol (version 7.0, 15 July 2021; US-specific) and the 2-year analysis SAP (version 2.0, 13 December 2021).

Background – The 2-year analysis of Study 270-301 was performed in January 2022 based on pre-specified analysis methods in the 2-year analysis SAP. Type B Pre-BLA feedback was received from FDA on 16 May 2022. FDA requested changes to the analysis methods, including primary and secondary endpoints. The results reported in 2-year 270-301 CSR reflect the modified analysis methods per FDA feedback and this CSR was submitted to the FDA on 29 September 2022, in the BLA re-submission. Changes from the planned analysis methods were documented in Section 9.8.2 of the CSR (Changes to Planned Analyses).

Solution – This NTF serves as a bridging document between the analysis methods in the 270-301 protocol (version 7.0, 15 July 2021; US-specific), the 2-year analysis SAP (version 2.0, 13 December 2021) and the 2-year 270-301 CSR.

The table below outlines all the changes made to the 2-year analysis methods, including primary and secondary endpoints

Changes to planned 2-yr Analyses for 270-301 based on FDA feedback			
	270-301 Protocol (version 7.0, 15 July 2021; US-specific)	2-year Analysis SAP (version 2.0, 13 December 2021)	270-301 2-Year CSR (in response to FDA Feedback)

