Sensitivity analysis: impact of exogenous FVIII product use in the efficacy evaluation period (EEP) on ABR	--	Not planned	
The following sensitivity analyses will be performed by counting exogenous FVIII product use in EEP as bleeding events:
 
 #1: count each one-time FVIII prophylaxis use in EEP as one bleed #2: count each one-time or routine FVIII prophylaxis use in EEP as one bleed 
#3: count each one-time or routine FVIII prophylaxis use and each surgery/procedure that had FVIII use in EEP as one bleed

Additional sensitivity analysis: impact of IS on ABR and FVIII activity	--	Not planned	
The following sensitivity analyses will be performed in subjects who have been off IS for at least 12 months
 
 Repeat the primary analysis of ABR (ABR

			change from baseline) in this subgroup Repeat the primary analysis of FVIII activity (FVIII activity change from baseline at Week 104) in this subgroup
Washout period between the last dose of FVIII prophylaxis following gene therapy and the start of EEP	No washout period	3 days	Based on the half-life of the original FVIII prophylaxis product: 
 • 3 days for standard half-life or plasma-derived products • 5 days for extended half-life
Definition of AEs/SAEs related to IS	--	All AEs/SAEs during or within 2 weeks' post-IS use	All AEs/SAEs following IS use up to each subject's last visit for the analysis
IS (CS or AIS) therapy to be included in the analysis	--	Systemic IS (CS or AIS) indicated for ALT elevation of any duration, or indicated for other purposes with a duration of at least 4 weeks	Systemic IS (CS or AIS) indicated for any purpose of any duration
Definition of an IS course (cycle)	--	The start of an IS use through the end of taper or increase in IS dose for ≥ 2 consecutive weeks preceded by at least 2 decreases in IS dose, whichever occurs earlier	The time period between the first day of starting an IS therapy to the last day of IS use. Any increase in the dose of IS will be considered as a new cycle of IS therapy with the first day of increase of IS dose constituting as the start day of a new cycle.

Comment(s)/ Recommendation(s):

This NTF serves as a bridging document between the analysis methods in the 270-301 protocol (version 7.0, 15 July 2021; US-specific), the 2-year analysis SAP (version 2.0, 13 December 2021) and the 2-year 270-301 CSR.

DocuSigned by:
PI
 Signer Name: **PI**

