9 DEMOGRAPHICS AND BASELINE CHARACTERISTICS

Subject demographic and baseline characteristics to be summarized include

- age at enrollment (year)
- age group (≥ 18 - < 65 , ≥ 65)
- age group (≥ 18 - < 30 , ≥ 30 - < 50 , ≥ 50)
- sex (Female/Male)
- ethnicity
- race
- height (cm)
- weight (kg)
- BMI (kg/m^2)
- baseline ECG evaluation
- history of liver disease (Yes/No)
- history of hepatitis B (Yes/No)
- history of hepatitis C (Yes/No)
- history of HIV (Yes/No)
- baseline disease characteristics including
 - time since diagnosis of hemophilia A (year)
 - type of FVIII treatment for hemophilia A (prophylaxis/episodic)
 - history of FVIII inhibitor (Yes/No)
 - FVIII genotyping results
 - number of target joints
 - body location of target joints
 - ambulatory assist device requirement (Yes/No)
- baseline FVIII activity (IU/dL) excluding values within 72 hours after a FVIII infusion

And for the following parameters, two sets of analyses will be performed to include data approximately 6-months (starting from Day 1 visit in study 270-902) or 12-months (starting from 6 months before Day 1 visit in study 270-902) prior to 270-301 study enrollment for study 270-902 rollover subjects, separately:

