11 PRIOR AND CONCOMITANT MEDICATIONS/PROCEDURES

Prior and concomitant medications are defined as follows:

- prior medication—any medication taken prior to the initiation of the investigational product and within 30 days prior to screening;
- concomitant medication—any medication taken after the initiation of the investigational product.

When a medication starts prior to the initiation of the investigational product and continues while on study, it will be summarized as both a prior and concomitant medication.

All medications will be coded using the current version of the World Health Organization Drug (WHO Drug) Dictionary.

Prior and concomitant medication use will be separately summarized by Anatomical Therapeutic Chemical (ATC) medication class (Level 4) and preferred name (i.e., generic medication name), and by NIH hepatotoxicity likelihood grades and preferred name as well. A subject reporting the same medication more than once will be counted once when calculating the number and percentage of subjects who received that medication.

Corticosteroid usage including total dose and total duration per subject, dose per corticosteroid course, duration per corticosteroid course, and time to corticosteroid course(s), and number of corticosteroid courses will be summarized for therapeutic purposes. Non-steroidal immunosuppressants may be summarized as well.

Baseline FVIII prophylaxis treatment will be summarized by type (extended half-life, standard half-life, and plasma derived) and drug preferred name.

Subjects who resume prophylactic treatment post BMN 270 infusion will be listed separately.

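### The 72-hour exclusion for FVIII activity samples ignores product half-life, while the Note to File sets a half-life-based washout for the start of the EEP; residual extended half-life factor may therefore enter some low activity values

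*SAP*

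**What the plan says.** **Activity rule.** SAP Section 13.3 states that post-BMN 270 "values for FVIII activity will be excluded from analysis if obtained within 72 hours" (3 calendar days if no time is recorded) "since the last infusion of exogenous FVIII replacement therapy". It makes no distinction by product. Section 9 and Appendix 20.1 footnote c apply the same 72 hours to measured baseline activity ("excluding values within 72 hours after a FVIII infusion").

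**Washout rule.** The Note to File, dated after SAP version 2.0, has a row headed "Washout period between the last dose of FVIII prophylaxis following gene therapy and the start of EEP". Its SAP column gives 3 days. Its CSR column, written after FDA feedback, gives "3 days for standard half-life or plasma-derived products" and "5 days for extended half-life". The Note says that "The table below outlines all the changes made to the 2-year analysis methods"; the activity exclusion is not in that table.

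**Product type.** Section 11 summarises baseline prophylaxis "by type (extended half-life, standard half-life, and plasma derived"), so the plan expects extended half-life users. It does not say how many.

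**Activity period.** Under Section 13.1 the primary chromogenic period starts on Day 33 and ends if routine FVIII prophylaxis resumes, defined as at least weekly use for 4 or more consecutive weeks. The supportive activity period has no such cut.

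**The concern.** The first-ranked secondary endpoint compares FVIII activity with no treatment, so its values should reflect transgene expression. By 5 days the reported analysis allows extended half-life product to have cleared before the EEP starts; the activity rule allows it 3 days. The rule that selects factor-level measurements is thus the less demanding of the two, although residual factor acts directly on those measurements.

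The samples concerned are those taken 72 to 120 hours after an extended half-life infusion given for a bleed, for a procedure, as one-time prophylaxis, as routine use too short to count as a restart, or as original prophylaxis continuing past Day 33. For all of these the 72-hour rule is the only protection.

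The results most exposed are those that turn on low values:

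- the proportions below 3 and from 3 to below 5 IU/dL (Section 13.3.2);
- the composite time-to-event analysis that requires two consecutive levels below 5 IU/dL before the first spontaneous treated bleed (Section 13.3.8), because a raised sample can break the sequence;
- the regression of bleeds in a window on activity in the same window (Section 13.3.4), because a treated bleed brings an infusion that can raise a later sample in that window.

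**Working it through.** **1. The plan's own figure.** Section 4.5 gives at least 95% power for the activity endpoint with N = 130, effect size 0.6, one-sample t-test, two-sided 0.05. The noncentrality is 0.6 × √130 = 6.84, and power from the noncentral t distribution exceeds 99.99%. The stated figure holds; 95% would already be reached at an effect size of about 0.32.

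**2. Residual exogenous factor.** The documents give no half-life, dose or post-infusion rise. Assumptions:

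- one-compartment decay, residual fraction = 2^(−t/h);
- standard half-life 12 h (range 8-14 h);
- extended half-life 5/3 of that, the ratio at which 5 days leaves the same fraction as 3 days: 20 h (range 13.3-23.3 h);
- initial rise 50-100 IU/dL.

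| Extended half-life | Left at 72 h | IU/dL at 72 h | Left at 120 h | IU/dL at 120 h |
|---|---|---|---|---|
| 13.3 h | 2.4% | 1.2-2.4 | 0.2% | 0.1-0.2 |
| 20 h | 2^(−3.6) = 8.2% | 4.1-8.2 | 2^(−6) = 1.6% | 0.8-1.6 |
| 23.3 h | 11.8% | 5.9-11.8 | 2.8% | 1.4-2.8 |

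For comparison, a standard product with a 12 h half-life leaves 2^(−6) = 1.6% at 72 h, or 0.8-1.6 IU/dL.

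The 72-hour column is the worst moment. At 20 h, the average fraction over 72-120 h is (20 / ln 2) × (0.0825 − 0.0156) / 48 = 4.0%, or 2.0-4.0 IU/dL.

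**3. Crossing the bounds.** Section 5.6 scores values below the LLOQ (3 IU/dL, Section 13.3.2) as 0. For a subject with no expression, at 20 h, the residual stays at or above 3 IU/dL until t = 20 × log2(rise/3): 81 h for a rise of 50 and 101 h for a rise of 100. It stays at or above 5 IU/dL until 20 × log2(100/5) = 86 h for a rise of 100; for a rise of 50 it is already below 5 at 72 h. So the bounds can be crossed, but only in part of the 48-hour interval. A subject whose true level is just under a bound needs less residual to cross it.

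**4. Frequency.** Each extended half-life infusion opens a 2-day gap. With k well-spaced infusions a year the share of days affected is 2k / 365.25: 0.5% for k = 1, 2.2% for k = 4, 6.6% for k = 12. The documents do not give the actual number of samples in the gap.

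**5. Week 104 mean.** The mITT population has 134 − 2 = 132 subjects. If n of them had their Week 104 median raised by 5 IU/dL, the mean rises by 5n/132: 0.04 for n = 1, 0.19 for n = 5, 0.38 IU/dL for n = 10.

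**The case against.** **SAP version 2.0 agrees with itself.** Its EEP washout is 3 days and its activity exclusion is 72 hours. The 5-day figure appears only in the Note's CSR column. This stands: the point is that one half-life-dependent rule was refined and a related one was not, not that the SAP contradicts itself.

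**A reader might infer that the plan treats the same factor as present for bleeding and absent for activity on days 4 and 5.** The documents do not support that. The 5-day washout governs a single gap per subject, before the EEP starts, and follows the original prophylaxis product. During the EEP, infusions for bleeds, procedures and one-time prophylaxis are handled by treatment policy (Section 13.2.1) and those days stay in the ABR. For such infusions the activity rule is stricter than the bleeding rule. The Note shows that the sponsor accepts half-life as relevant to washout; it is not a precedent for dropping individual samples.

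**A reader might also infer that exogenous factor is in fact being counted as expression, mostly in low expressors.** Neither is documented. The numbers of extended half-life users and of samples in the 72-120 hour gap are not given. Section 13.3.4 cites an association between higher activity and fewer bleeds, which makes a concentration in low expressors plausible but does not establish it.

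**There are safeguards.** The primary activity period ends when routine prophylaxis resumes, each subject's value is a window median, maximum FVIII is taken over window medians, and a residual that leaves the total below 3 IU/dL still scores 0. These limit the effect without removing it. Isolated or short use does not count as a restart, and after Week 52 each Appendix 20.1 window lists one scheduled day (Day 730 for Week 104), so the median may rest on a single sample.

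**Conclusion.** The activity exclusion is not aligned with the half-life-based washout in the Note to File, and values taken 72-120 hours after an extended half-life infusion may include residual exogenous factor. That the two rules differ is plain from the text; the size of any bias rests on assumed half-lives and rises. On those assumptions the residual at 72 hours is about 4-8 IU/dL at a 20-hour half-life and about 1-12 across 13-23 hours, and it falls quickly after that.

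The Week 104 mean would probably move by tenths of an IU/dL. Its test, against an imputed baseline of 1 IU/dL, is unlikely to change: power is above 99.99% at the planning effect size, and Section 13.7 reports p < 0.0001 for all pre-specified tests at 1 year. The practical exposure is in the low-activity categories, the below-5 event definition and the activity-bleeding analyses. This is a cheap improvement, not a threat to the main conclusion.

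**What to change.** In Section 13.3, for post-BMN 270 activity values, make the exclusion depend on the product actually infused: 72 hours (3 calendar days) after standard half-life or plasma-derived FVIII, and 5 days after extended half-life FVIII, in line with the Note to File. Apply it to the Week 104 analysis, the visit-window summaries, maximum FVIII, and Sections 13.3.4 and 13.3.8. Keep the uniform 72-hour rule as a sensitivity analysis; at minimum, run the product-specific rule as the sensitivity analysis. In either case report how many samples and subjects are affected.

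Leave the measured-baseline rule (Section 9, Appendix 20.1 footnote c) unchanged. The endpoint baseline is imputed as 1 IU/dL (Section 5.5), so changing it cannot affect the endpoint. Subjects do not stop prophylaxis before dosing, so a longer exclusion could leave few measured baselines in extended half-life users.

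The cost is a wording change and one programming flag. Sections 11 and 13.5.1 already plan summaries by product type, so the data should be available. A few more values will be excluded and handled by the rules in Sections 5.6 and 13.3.1, and the mean may become slightly less favourable.
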